## Clinical Investigation Plan

**Figure 5. Study Flow Diagram**

## Clinical Investigation Plan

### 3.2 Measures Taken to Avoid and Minimize Bias

Multiple measures will be taken to avoid and minimize bias in this clinical investigation. First, TactiFlex PAF IDE is a prospective clinical investigation in which the outcome is unknown at the time of enrollment and all subjects must meet the defined eligibility criteria to minimize selection bias. Next, guidance will be provided to sites regarding data collection for questionnaires and the post-procedure follow-up phone calls to be performed at 7-days, 5-weeks, and 6-months post-procedure. Additionally, case report forms for data collection will be provided to sites, which will minimize inter-observer variability.

Evaluation of primary endpoint data will be performed by an independent core laboratory and Clinical Events Committee (CEC). Collected electrocardiogram (ECG), trans-telephonic monitoring (TTM), and 24-hour Holter data from sites will be evaluated by a physician at a core laboratory to determine AF recurrence for subjects. To ensure consistent monitoring for arrhythmia recurrence across the subject population, it is required (as permitted by local regulations) that either the core lab or site personnel contact the subjects to help them perform each scheduled TTM transmission and verify that the transmission has been received by the core lab.

A CEC made up of physicians who are not investigators in the trial will be used to adjudicate all AEs that are determined by the Sponsor's Safety group to potentially meet the criteria of 1) a serious AE and/or 2) an AE related to the investigational devices or ablation procedure. To minimize bias, only the core lab and the CEC's adjudication of the collected data will be used for the analysis of the primary safety endpoint.

Protocols are also in place to minimize lost to follow-up subjects (**Section 5.5.1**). Sensitivity analyses will be performed demonstrating the impact missing data may have on the trial.

An independent Data Safety Monitoring Board (DSMB) will be established (**Section 10.9.3**) and serve in an advisory role to the Sponsor to ensure safety by reviewing cumulative data from the clinical investigation at prescribed intervals for the purpose of safeguarding the interests of enrolled subjects and those patients yet to be enrolled, as well as the continuing validity and scientific merit of the clinical investigation.

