## Clinical Investigation Plan

recurrence 31-80 days after the initial procedure and will not be considered a treatment failure. Failure to achieve acute procedural success (confirmation of entrance block after a 20-minute minimum waiting period) during the last ablation procedure with the TactiFlex SE catheter will constitute failure to achieve this endpoint. After the 90-day blanking period, use of Class I or III AADs will not count as a therapy failure provided that only previously failed Class I or III AADs are taken at doses that do not exceed the previously failed dose.

AF/AFL/AT recurrence will only be assessed by 12-lead ECG, TTM, and Holter monitoring devices for assessment of this primary endpoint so that all subjects are monitored equally with devices of the same sensitivity and specificity (recurrence data collected from other devices such as pacemakers, ICDs, or ICMs will not be included in the assessment). ECG, TTM, and Holter data collected from sites will be evaluated by a core laboratory to ensure independent and unbiased assessment of AF/AFL/AT recurrence for endpoint analysis.

There are multiple situations in which subjects will be considered primary effectiveness endpoint failures:

- If the subject fails to achieve acute procedural success, defined as confirmation of entrance block in all pulmonary veins after a minimum waiting period of 20-minutes, during last ablation procedure performed with the TactiFlex SE catheter, or
- If documented AF/AFL/AT recurrence (>30 second episode) occurs at any time after the blanking period (>90 days after the initial procedure), or
- If the subject requires a repeat procedure for the treatment of AF >80 days after the initial procedure, the subject will be considered an effectiveness endpoint failure regardless of documentation of a >30 second AF/AFL/AT episode, or
- If the subject requires a second repeat AF ablation procedure ≤80 days after the initial procedure, or
- Any use of a new class I or III AAD for AF after the blanking period, or
- Any use of a class I or III ADD for AF at a dose higher than that previously failed by the patient, or
- If the subject requires a cardioversion (electrical or pharmacological) for the treatment of AF after the blanking period, or

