- If the subject has a continuous atrial arrhythmia throughout a 12-lead ECG recording after the blanking period indicating AF/AFL/AT recurrence, this will be considered sufficient documentation of recurrence unless there is evidence that the recorded arrhythmia is short-lived and less than 30 seconds as determined by the investigator, or
- Any ablation in the left atrium using an ablation catheter other than TactiFlex SE.

Cavotricuspid isthmus (CTI)-dependent AFL that occurs alone either during or after the blanking period will be considered an exception to being considered a recurrence, as CTI-dependent AFL is easily treated with cavotricuspid isthmus ablation and is not an iatrogenic arrhythmia following a left atrial ablation procedure for AF. Occurrence of CTI-dependent AFL confirmed by entrainment maneuvers that occurs at any time during the follow-up period and is ablated, will not be considered a primary effectiveness endpoint failure.

The performance goal (PG) is set at 50% based on the chronic acceptable success rate for paroxysmal AF at 12-months in the 2017 Consensus Statement [17]. The 50% chronic acceptable success rate

---

 For subjects that have a repeat ablation procedure ≤80 days after the initial procedure, only failure to achieve acute procedural success during the repeat procedure will contribute to primary effectiveness endpoint.

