### **3-Month (91 + 14 days) Follow-Up Visit**

The 3-month follow-up visit is a scheduled in-person site visit.

- 12-lead ECG
- Document AAD and anticoagulant usage
- Administer the AFEQT and EQ-5D-5L questionnaires
- Document adverse events and protocol deviations
  - If the subject describes symptoms suggestive of pulmonary vein stenosis (e.g. shortness of breath, cough, and hemoptysis), complete CT or MRI imaging of pulmonary veins.
  - If the subject describes symptoms suggestive of cardiac tamponade (i.e., chest pain with hypotension) or if cardiac tamponade is suspected, the subject should be evaluated promptly by the investigator and a TTE performed.
- Provide the subject with a TTM device (regardless of having an implantable device capable of recording ECGs such as an ICM/ILR, pacemaker, or ICD) for scheduled heart rhythm transmissions and transmission of symptomatic episodes.
  - The first scheduled TTM transmission is to be within the 14-day period following the 3-month visit (1-14 days after the visit). At least one TTM transmission must occur in every 14-day period between the 3-month and 12-month follow-up visits (1-14, 15-28, 29-42, 43-56, etc. days after the 3-month visit). As permitted by local regulations, it is recommended that either the core lab or site personnel contact the subjects to help them perform each scheduled TTM transmission and verify that the transmission has been received by the core lab.

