## Clinical Investigation Plan

### 6.7 Core Laboratory

A core lab will be used for the collection, interpretation, and collation of data collected from the following sources:

- TTM
- 24-hour Holter monitoring
- 12-lead ECGs

The core lab will provide independent review of this data by appropriately trained personnel using standardized procedures to interpret TTM, 24-hour Holter, and 12-lead ECG tracings for adjudication of atrial arrhythmias. Findings will be communicated to the investigator and to Abbott. The core lab's adjudication findings will be used for analysis of effectiveness outcomes.

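### The site investigator, not the core lab, decides whether a continuous arrhythmia on a post-blanking 12-lead ECG lasted under 30 seconds, and no visible text says whose finding prevails

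*Protocol*

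**What the plan says.** Protocol 4.1.2 and SAP 1.4.1.2 list nine situations that make a subject a primary effectiveness failure. The eighth concerns a continuous atrial arrhythmia throughout a 12-lead ECG recorded after the blanking period. Failure is the default, and the ECG is sufficient documentation of recurrence "unless there is evidence that the recorded arrhythmia is short-lived and less than 30 seconds as determined by the investigator". The wording is the same in both documents.

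Elsewhere the plan gives rhythm recurrence to an independent reader:

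- Protocol 3.2: ECG, TTM and Holter data "will be evaluated by a physician at a core laboratory to determine AF recurrence for subjects".
- Protocol 4.1.2, repeated in SAP 1.4.1.2: these data "will be evaluated by a core laboratory to ensure independent and unbiased assessment of AF/AFL/AT recurrence for endpoint analysis".
- Protocol 6.7: the core lab's "adjudication findings will be used for analysis of effectiveness outcomes". The inputs listed there are TTM, 24-hour Holter and 12-lead ECGs.

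Two further statements bear on the point. Protocol 3.2 has one exclusive rule, that "only the core lab and the CEC's adjudication of the collected data will be used for the analysis of the primary safety endpoint"; it names safety only. Protocol 6.7 also says of the core lab: "Findings will be communicated to the investigator and to Abbott".

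**The concern.** The trial has a single arm and is judged against a fixed 50% effectiveness goal. For rhythm-based failures, the plan's stated protection against bias is independent reading. In this one criterion the endpoint definition names the treating site as the party that decides duration, and that decision removes the ECG as a failure. What matters here is independence rather than blinding, because every reader knows that there is only one treatment.

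Suppose the core lab reads an ECG as recurrence and the investigator holds that it lasted under 30 seconds. One analyst could follow Protocol 6.7 and count a failure. Another could follow the specific clause in 4.1.2 and count none. Both would be following the text. The visible text also does not say whether the investigator may invoke the exception after the core-lab reading has been sent back. An exception made in error can only move a subject towards success.

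**Working it through.** The plan gives no figure to reproduce on this point, and the sample-size sections are redacted. The check is therefore a comparison of texts, followed by arithmetic for scale.

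**1. Which rule governs?**

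| Place | Who decides | Scope |
|---|---|---|
| Protocol 4.1.2 and SAP 1.4.1.2, eighth criterion | Investigator | Duration under 30 seconds on a post-blanking 12-lead ECG |
| Protocol 3.2 | Core-lab physician | AF recurrence from ECG, TTM and Holter |
| Protocol 4.1.2 and SAP 1.4.1.2, general text | Core lab | Recurrence for endpoint analysis |
| Protocol 6.7 | Core lab | Findings used for effectiveness |
| Protocol 3.2, exclusive rule | Core lab and CEC only | Primary safety endpoint |

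The general rules do not mention the exception, and the exception does not mention the core lab. Protocol 6.7 does not list a site's separate evidence of duration among the core lab's inputs.

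**2. How often can the clause apply?**

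Scheduled 12-lead ECGs fall at 3 and 12 months, and unscheduled visits may add others. The visit text in Protocol 6.6.3 sets the 3-month visit at 91 + 14 days, so both scheduled ECGs come after blanking. Table 4 gives 91 ± 14 days, so the visit can be as early as 91 − 14 = day 77. Blanking runs to day 90, and in that case only one scheduled ECG is exposed.

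**3. What else can still catch the subject?**

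"At least one TTM transmission must occur in every 14-day period between the 3-month and 12-month follow-up visits". With the windows in Protocol 6.6.3, the interval between the two visits holds:

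- nominal: (365 − 91)/14 = 19.6, so 19 complete periods
- shortest: (335 − 105)/14 = 16.4, so 16
- longest: (395 − 91)/14 = 21.7, so 21

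A 24-hour Holter follows at 12 months. This backstop is substantial after a 3-month ECG. It is thin after a 12-month ECG, because the TTM device is collected at that visit and the Holter is the only scheduled recording left.

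**4. Size, for illustration**

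Let k be the number of subjects with a wrongly excepted ECG and q the share of them who fail on another criterion anyway. Both are assumptions. As a simple proportion of the 305 planned main-study subjects:

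shift in percentage points = 100 × k × (1 − q) / 305

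| | k = 1 | k = 3 | k = 5 |
|---|---|---|---|
| q = 0 | 0.33 | 0.98 | 1.64 |
| q = 0.5 | 0.16 | 0.49 | 0.82 |
| q = 0.8 | 0.07 | 0.20 | 0.33 |

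The planned estimate is Kaplan-Meier, so these are orders of magnitude only. A subject who fails later is still a 12-month failure, and only the event time moves.

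**The case against.** The strongest reply is that Protocol 6.7 already settles the matter. It is unqualified, it covers 12-lead ECGs, and it says core-lab findings are what the effectiveness analysis uses. On that reading the investigator supplies evidence of duration and the core-lab finding is analysed. This is plausible, and the general rules do favour it. It does not dispose of the point, because the clause naming the investigator is the more specific one, sits inside the endpoint definition, and is not ranked against 6.7 in any visible text.

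It is also fair to say that the criterion is conservative by default. It accepts a continuous arrhythmia as recurrence without a measured 30 seconds, and the exception needs evidence and only restores the endpoint's own threshold of more than 30 seconds. A truly short arrhythmia with no evidence of its duration would be counted as a failure, which is an error in the other direction. This stands, and it confines the concern to wrong exceptions.

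A reader might infer from the safety-only exclusive rule in Protocol 3.2 that effectiveness was deliberately left without core-lab protection. The documents do not support that. The same section gives evaluation of primary endpoint data to the core lab and CEC together, and the core lab's listed inputs are rhythm recordings, so the narrow wording may be a drafting slip. The sentence simply does not settle precedence for effectiveness.

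Nor should one infer that the core lab protects the other eight criteria. Those on antiarrhythmic drugs, cardioversion and repeat ablation rest on treatment decisions.

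**Conclusion.** The conflict is real and narrow. For one failure criterion, both documents name the investigator as the one who determines duration, while the general rules assign ECG recurrence to the core lab, and no visible text says which governs when they differ. The three powered secondary endpoints and the HSP substudy endpoints are defined by reference to the primary ones, so they inherit the clause.

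The severity is minor. The effect cannot be sized from the documents. It is 0.33 points per wrongly excepted subject who never fails otherwise, assuming all 305 main-study subjects are analysed as a simple proportion. Nothing in the documents shows that even one such exception would occur.

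A reader might infer that recurrence escapes core-lab review, or that the success rate will be materially inflated. Neither is supported. The core lab is to read these ECGs, correct use of the exception is not bias, and TTM and Holter recurrences are outside the clause.

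A precedence rule may exist where the text is redacted (within Protocol 4.1.2, in Protocol 8.2.1.2, and in SAP 2.3.1, 2.13.1 to 2.13.3 and 2.14) or in core-lab procedures that are not available here.

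**What to change.** 1. In Protocol 4.1.2 and SAP 1.4.1.2, replace the investigator's determination with: *as determined by the core laboratory on review of the ECG and any duration evidence submitted by the site*. State that the ECG counts as recurrence if the core lab does not confirm a duration under 30 seconds.
2. Limit this precedence statement to this criterion. The exception for CTI-dependent flutter rests on entrainment manoeuvres and ablation and should stay as it is.
3. Add site-submitted evidence of duration to the core-lab inputs in Protocol 6.7.
4. Report the number of excepted ECGs. Optionally, add a sensitivity analysis that counts them as failures, labelled as a conservative bound because it would also count arrhythmias that truly lasted under 30 seconds.

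If a precedence rule already exists in redacted text or core-lab procedures, stating it in both sections would resolve the ambiguity.

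The cost is wording in both documents, a small extension of the core lab's remit and procedures, forwarding of evidence by sites, and a few extra items for the core lab to review. The success rate may be slightly less favourable where the core lab does not confirm a short duration.

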### 3.1 Clinical Investigation Procedures and Follow-up Schedule

The visit schedule for subjects is shown in **Figure 5**. Once eligibility is confirmed, the subject will undergo a study ablation procedure for treatment of their PAF condition. A blanking period of 90-days will be employed after the initial ablation procedure, followed by a 9-month evaluation period. The total follow-up period will be for 12 months. Medication adjustments, cardioversions, and one repeat ablation procedure may be performed in the blanking period without being considered a primary effectiveness endpoint failure (repeat ablation for AF must be performed 31-80 days after the initial procedure). Subjects must be off Class I and III antiarrhythmic drugs (AADs) after the blanking period, unless clinically justified. Follow-up assessments will occur either in-person at the clinic or via phone contact after the procedure. The scheduled follow-up visits will occur before the patient leaves the hospital and then at 7-days (phone call), 5-weeks (phone call), 3-months (in-person visit), 6-months (phone call), and 12-months (in-person visit) after the initial procedure. The subject will be exited from the trial after completing their 12-month follow-up visit.

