### 4.0 ENDPOINTS

#### 4.1 Primary Endpoints and Rationale

##### 4.1.1 Primary Safety Endpoint

The primary safety endpoint is the rate of device and/or procedure-related serious adverse events with onset within 7-days of any ablation procedure that uses the TactiFlex SE catheter (initial or repeat procedure performed 31-80 days of initial procedure) that are defined below:

- Atrio-esophageal fistula
- Cardiac tamponade/perforation
- Death
- Heart block
- Myocardial infarction
- Pericarditis
- Phrenic nerve injury resulting in diaphragmatic paralysis
- Pulmonary edema
- Pulmonary vein stenosis
- Stroke/cerebrovascular accident
- Thromboembolism
- Transient ischemic attack
- Vagal nerve injury/gastroparesis
- Vascular access complications (including major bleeding events)

. Atrio-esophageal fistula, cardiac tamponade/perforation and pulmonary vein stenosis will be evaluated through 12-months.

. Bleeding is a major complication of AF ablation if it requires and/or is treated with transfusion or results in a 20% or greater fall in hematocrit.

These events must meet the criteria listed in **Appendix II** to be included in the primary endpoint as adjudicated by the Clinical Events Committee (CEC).

The performance goal for the Primary Safety Endpoint for this clinical trial

= 12.9%.

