### **6.6.4 Repeat Ablation Procedures**

One ablation procedure is allowed during the blanking period (between 31 and 80 days post-initial procedure) due to AF/AFL/AT recurrence without being considered an effectiveness endpoint failure. The repeat procedure must be performed with the TactiFlex SE catheter using the recommended parameters listed in the *Instructions for Use* document and in **Section 6.3**. The TactiFlex SE catheter cannot be used for repeat procedures that occur  $\geq 81$  days after the initial procedure or if the subject requires a third ablation procedure at any time during the follow-up period (a marketed ablation catheter should be used).

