- If the subject requires a second repeat AF ablation procedure ≤ 80 days after the initial procedure, or
- Any use of a new class I or III AAD for AF after the blanking period, or
- Any use of a class I or III ADD for AF at a dose higher than that previously failed by the patient, or
- If the subject requires a cardioversion (electrical or pharmacological) for the treatment of AF after the blanking period, or
- If the subject has a continuous atrial arrhythmia throughout a 12-lead ECG recording after the blanking period indicating AF/AFL/AT recurrence, this will be considered sufficient documentation of recurrence unless there is evidence that the recorded arrhythmia is short-lived and less than 30 seconds as determined by the investigator, or
- Any ablation in the left atrium using an ablation catheter other than TactiFlex SE.

¹ For subjects that have a repeat ablation procedure ≤ 80 days after the initial procedure, only failure to achieve acute procedural success during the repeat procedure will contribute to primary effectiveness endpoint.

Statistical Analysis Plan

Cavotricuspid isthmus (CTI)-dependent AFL that occurs alone either during or after the blanking period will be considered an exception to being considered a recurrence, as CTI-dependent AFL is easily treated with cavotricuspid isthmus ablation and is not an iatrogenic arrhythmia following a left atrial ablation procedure for AF. Occurrence of CTI-dependent AFL confirmed by entrainment maneuvers that occurs at any time during the follow-up period and is ablated, will not be considered a primary effectiveness endpoint failure.

Counting the use of new or higher than previously failed doses of AADs after the blanking period as effectiveness failures is consistent with the primary effectiveness endpoint recommendations in the FDA Guidance on Clinical Study Designs for Percutaneous Catheter Ablation for the Treatment of Atrial Fibrillation [14].

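### The repeat-ablation windows conflict: a TactiFlex SE repeat on days 1-30 can replace a failed index result, and 11 of 14 safety event types may go uncounted after it

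*Protocol*

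**What the plan says.** **Permission.** Protocol 3.1 states that "repeat ablation for AF must be performed 31-80 days after the initial procedure". Protocol 4.1.2 allows one repeat for "recurrence 31-80 days after the initial procedure and will not be considered a treatment failure". Protocol 6.6.4 gives the same window, "between 31 and 80 days post-initial procedure", and Protocol 6.5, Appendix X and SAP 1.4.1.2 agree.

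**Acute success.** Protocol 4.1.2 judges entrance block at the last procedure done with TactiFlex SE. Footnote 1 to that sentence begins "For subjects that have a repeat ablation procedure ≤80 days after the initial procedure, only failure to achieve acute procedural success during the repeat procedure" and makes this the only acute result that contributes. SAP 1.4.1.2 has the same footnote ("only failure to achieve acute procedural success during the repeat procedure will contribute to primary effectiveness endpoint"), as does Appendix X.

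**Failure list.** Three items in Protocol 4.1.2 and SAP 1.4.1.2 concern further ablation: a repeat for AF after day 80; "If the subject requires a second repeat AF ablation procedure ≤80 days after the initial procedure"; and left atrial ablation with a different catheter at any time. Protocol 6.6.4 bars TactiFlex SE from day 81 and from a third procedure. It has no matching sentence for days 1-30.

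**Safety.** Protocol 4.1.1, Appendix X and SAP 1.4.1.1 and 2.3.1.1 start the 7-day window at every ablation done with TactiFlex SE, then add a parenthesis that in Protocol 4.1.1 reads "initial or repeat procedure performed 31-80 days of initial procedure". A footnote to the event list follows atrio-esophageal fistula, tamponade/perforation and pulmonary vein stenosis through 12 months.

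**The concern.** The permission, the footnote, the failure list and the safety parenthesis each use a different window, and a first TactiFlex SE repeat on days 1-30 falls between them. It is not exempt, it is not named as a failure, the footnote lets it replace the index result, and the safety parenthesis leaves it out.

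Two programmers working from the same text could score the same subject differently on either co-primary endpoint. Because the study is single-arm and compared with fixed performance goals, there is no control group in which such scoring would cancel out. The study succeeds only if both null hypotheses are rejected, so both definitions need to be unambiguous before the data are seen.

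**Working it through.** The point concerns definitions, so there is no planned figure to reproduce. The sample-size assumptions are redacted, and N = 305 is taken as given.

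**Step 1. The windows for a first repeat with TactiFlex SE.**

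| Rule | Days 1-30 | Days 31-80 | After day 80 |
|---|---|---|---|
| Exempt from failure (Protocol 3.1, 4.1.2, 6.5, 6.6.4) | No | Yes, once | No |
| Named in the failure list (Protocol 4.1.2, SAP 1.4.1.2) | **No** | No | Yes, if for AF |
| Footnote 1 replaces the index acute result | **Yes** | Yes | No |
| Opens a 7-day safety window under the parenthesis | **No** | Yes | No |

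The days 1-30 column is inconsistent. The days 31-80 column is coherent and is the stated design. After day 80 only the safety row is open, and only if the catheter is used against Protocol 6.6.4.

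**Step 2. Illustrative subjects, effectiveness** (no later failure event in either).

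- Index procedure fails entrance block; TactiFlex SE repeat on day 10 succeeds. The last TactiFlex SE procedure was a success, footnote 1 looks only at the repeat, the repeat is not after day 80, there is no second repeat, and no other catheter was used. No item is met, so the subject can finish as a success.
- Index procedure succeeds; TactiFlex SE repeat on day 10 fails entrance block. Footnote 1 scores the subject on the repeat: a failure.

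**Step 3. Illustrative subjects, safety** (events adjudicated as device- or procedure-related).

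- Repeat on day 20, stroke on day 22. Onset is 22 - 20 = 2 days after the repeat and 22 days (more than 7) after the index procedure. It counts under the opening phrase but not under the parenthesis.
- Same timing, tamponade. It counts, because that event type is evaluated through 12 months.
- Repeat on day 3, stroke on day 5. It counts, because onset is within 7 days of the index procedure.

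The list has 14 event types and 3 have the 12-month window, so 14 - 3 = 11 types are exposed when onset is more than 7 days after the index procedure.

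**Step 4. Scale.** One subject is 1/305 = 0.33 percentage points; three are 3/305 = 0.98 points. For orientation, exact binomial boundaries were computed at N = 305 with no attrition. The one-sided alpha is an assumption, shown at two values.

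| Goal | Alpha 0.025 | Alpha 0.05 |
|---|---|---|
| Safety 12.9%: most events allowed | 27 (8.9%) | 29 (9.5%) |
| Effectiveness 50%: fewest successes needed | 171 (56.1%) | 168 (55.1%) |

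With 275 to 290 evaluable subjects the safety limit is 24 to 27 events. The planned effectiveness analysis is Kaplan-Meier, so that boundary is approximate. A few reclassified subjects would change a conclusion only near these boundaries.

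**The case against.** The strongest reply is that this is a wording mismatch with little reach. Only days 31-80 are exempt, so an earlier repeat has no protection, and the failure list is introduced as a set of situations without being called exhaustive. A reader could infer failure. That reading is available, but the list does not state it and footnote 1 points the other way.

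Several limits stand, and they rule out stronger readings that a reader might infer:

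- *All complications of an early repeat escape the safety count.* They do not. Three event types run through 12 months, and any listed event within 7 days of the index procedure counts. The opening phrase also supports inclusion, so the text contradicts itself rather than plainly excluding.
- *Any early repeat escapes the failure list.* Left atrial ablation with another catheter is already a failure at any time.
- *The effectiveness gap also exists after day 80.* It does not: a repeat for AF is then a listed failure and footnote 1 stops at day 80.
- *The footnote always favours the device.* It can also turn an index success into a failure, and recurrence, cardioversion or new antiarrhythmic drug use after blanking still counts.
- *The plan has no rule for such repeats.* The analysis populations and parts of the endpoint analyses are redacted and may contain one.

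The powered single-procedure endpoint counts every left atrial repeat as a failure, so it is unaffected. Repeat ablations and procedure-related adverse events are also reported descriptively. This gives visibility but does not settle how the primary endpoints are scored.

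**Conclusion.** The visible endpoint definitions are wrong as written, with a small expected impact. A first TactiFlex SE repeat on days 1-30 lies outside the exemption, is not a named failure, and can replace a failed index result. Read literally, the safety parenthesis also omits 11 of 14 event types after such a repeat, or after use past day 80 by deviation, when onset is more than 7 days after the index procedure. For safety, the literal reading can only lower the event rate.

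The size is 0.33 points per affected subject, assuming all 305 are analysed. The net effect cannot be computed, because no expected frequency of such repeats is given. Nothing in the documents supports a claim that either test result would change. The point is worth correcting because the scoring of a co-primary endpoint should not depend on which sentence is followed.

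**What to change.** Make the same changes in Protocol 4.1.1, 4.1.2 and Appendix X, and in SAP 1.4.1.1, 1.4.1.2 and 2.3.1.1:

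1. Restrict footnote 1 to repeats on days 31-80.
2. State that a left atrial repeat on days 1-30 is outside the exemption and counts as a primary effectiveness failure. This follows from the stated exemption, and it settles the case even where the body text still refers to the last TactiFlex SE procedure. Limiting it to the left atrium leaves the exception for CTI-dependent flutter intact.
3. Reconcile the safety parenthesis with the opening phrase, so that listed events with onset within 7 days of any procedure using TactiFlex SE count, whatever the day.

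If a redacted section already holds a rule, align the definitions with it. These changes concern endpoint counting only, not when a patient may be re-ablated.

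The cost is wording. No new data are needed: adverse events are collected from consent (Protocol 7.3.1), and a 7-day contact follows each ablation (Protocol 6.6.3). The downside for the sponsor is that either rate may become slightly less favourable.
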